Qsymia provides a potential opportunity to develop an effective treatment plan that would be an adjunct to surgical intervention in the super obese patient. Use of Qsymia in addition to a low-calorie dietary prescription pre-operatively would effectively decrease weight prior to surgical intervention, lowering surgical risk to some extent. Additionally, if continued post-operatively, Qsymia as an adjunct to the post-surgical dietary plan would potentially extend the weight loss horizon so that the probability of the typical weight loss plateau at 12-18 months is decreased. The combination of the pre-operative and post-operative weight loss associated with Qsymia use could significantly diminish the need for a second surgical procedure in super obese patients. We have designed a pilot study to examine the use of Qsymia in super obese patients to determine its potential for decreasing the need for a second weight loss surgery.

Primary Objective

The primary objective of the proposed study is to demonstrate the effectiveness of using Qsymia in the superobese (BMI ≥ 50 kg/m²) as an adjunct to surgical therapy.

Secondary Objectives

Secondary objectives of the proposed study include determining tolerability of Qsymia perioperatively, determining changes in resting metabolic rate postoperatively (3 months and 12 months post-surgery), determining the magnitude of preoperative weight loss and determining the magnitude of weight loss at 12, 18, and 24 months post-surgery.

Treatment Plan

Treatment Group

Patients with a BMI ≥ 50 kg/m² that agree to participate in the experimental group will begin their treatment plan with a medical weight loss diet that includes a low-calorie diet and Qsymia at the recommended treatment dose of 7.5/46 mg daily (following initiation of the titration dose for 2 weeks). The low-calorie diet will be individually tailored based on initial resting metabolic rate measurement and co-morbid conditions. Patients will be medically monitored with once monthly medical visits and also have once monthly visits with a dietitian to review the treatment plan. Patients will receive medical weight loss therapy for a minimum of 3 months prior to proceeding to the laparoscopic sleeve gastrectomy. If a patient opts not to proceed to sleeve gastrectomy, they will continue to receive medical therapy for weight reduction including Qsymia and followed for the duration of the study (i.e., for 2 years).

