Patients will discontinue Qsymia the week prior to the scheduled operation. The sleeve gastrectomy will be performed by one of the surgeons at the Weight Management Center ([name], [name], [name]) using standard laparoscopic technique. Post-operatively, all patients will be provided with dietary counseling and a nutrition prescription for a very low calorie, high protein diet: 500-700 calories, protein goal of 1-1.2g/kg IBW, and 60-75g carbohydrate. Qsymia will be resumed in the second post-operative week at the initial titration dose and increased to the recommended treatment dose of 7.5/46 mg daily. Patients will have standard post-operative surgical follow up at months 1, 3, 6, 9, 12, 18, and 24. During the post-operative phase, all patients will be enrolled in the bariatric support group program that meets on a monthly basis. Patients will also have at least 3 visits with a clinic dietitian to review and update dietary prescriptions. At any point during this course of follow up, a determination can be made that the primary outcome event has occurred if the patient has a weight plateau—defined as weight gain or < 3 lbs weight loss—for 3 consecutive months, remains above a BMI of 39.9 kg/m² and continues to have associated co-morbidities. These patients will be evaluated for the possibility of moving forward to the next operative stage (laparoscopic Roux-en-Y gastric bypass) while all other patients will continue on with medication and diet/exercise therapy.

Control Group

Control subjects for the proposed study will be identified from the patient population at the Wake Forest Baptist Health Weight Management Center. They will be matched to subjects in the treatment group on age, sex, ethnicity, and BMI. They will be a historical control group who had surgery prior to the commencement of the proposed study (retrospective review).

Trial Design

Prospective independent historical case control

Inclusion Criteria

Inclusion criteria for the proposed study are:

- BMI \geq 50 kg/m²
- Determined to be a good candidate for surgery based on medical and psychological exam.
- Willing to participate in a 3-6 month medically supervised weight loss plan prior to surgery.
- Planning to remain in the reasonable vicinity of the Wake Forest Baptist Health Weight Management Center for the duration of the study.

Exclusion Criteria

- History of prior weight loss surgery (removal/conversion from band to sleeve will not be excluded)

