- Pregnant (women of childbearing potential will complete a pregnancy test (blood draw) to make sure they are not pregnant at the time that they initiate the medication). Ongoing monitoring of pregnancy status is the responsibility of the patient and they are instructed as such in the consent form.
- Ongoing use of weight loss medication
- Contraindications to use of Qsymia, including pregnancy, history of glaucoma, unstable cardiac disease (unstable angina, recent heart attack or stroke (in the past 6 months), uncontrolled arrhythmia), hyperthyroidism, taking MAOIs (monoamine oxidase inhibitors) or allergy to either topiramate or sympathomimetic amines like phentermine.

Patients may be removed from the study at any point if they are unable to tolerate the study medication or are less than 50% compliant with the study medication (take less than 50% of the recommended dose). If a patient is removed from the study due to medication intolerance or non-compliance, the study physician will meet with them and instruct them on how to stop the medication.

Primary endpoint

The primary endpoint for this study is the proportion of patients that meet the criteria to move forward with the second surgical procedure (Roux en Y Gastric Bypass). The criteria include all of the following at any point in the 24 month post-surgical follow up period:

1. Weight plateau (defined as weight gain or < 3 lbs weight loss) for at least 3 months
2. Remains above a BMI of 39.9 kg/m²
3. Continues to have obesity associated co-morbidities (Co-morbidities include hypertension, type 2 diabetes mellitus or pre-diabetes, hyperlipidemia, metabolic syndrome, obstructive sleep apnea, osteoarthritis, non-alcoholic steatohepatitis (NASH), gastroesophageal reflux disease (GERD)).

We hypothesize that the study group treated with Qsymia plus surgery will have a lower rate of occurrence of the primary endpoint at 24 months post-surgery compared to the group with surgery only.

Secondary endpoints

The secondary endpoints for this study are percent weight loss both before and after surgery and changes in percent body fat and resting metabolic rate.

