We hypothesize that the study group treated with Qsymia plus surgery will have greater percent weight loss at all time points compared to the group treated with surgery only. We also hypothesize that the study group treated with Qsymia plus surgery will have a higher resting metabolic rate after adjustment for lean body mass compared to the group treated with surgery only.

Other measures obtained by chart review

Height will be measured at all new patient visits and will be repeated at 24 months to account for any changes over the course of participation. Weight is measured at every clinic visit and will be captured for the study at the time points in the table below. Waist circumference will be measured at the level of the umbilicus at the time points reported in the table. Resting metabolic rate will be measured using expired gas analysis via the MEDGem analyzer. This will be measured following the protocol suggested by the manufacturer, including after refraining from eating, drinking, caffeine or exercise for at least 4 hours prior and immediately following a 10 minute period of quiet rest. Body fat percentage will be measured using Bioelectrical Impedance Analysis via the RJL Systems Quantum II. The Quantum II provides body fat percentage as well as a calculation of total lean mass and total fat mass.

Blood Measures

Blood will be drawn at baseline, 3 months, 6 months, 12 months, 18 months and 24 months and stored for use in later analysis.

Boxes marked with UC are tests that are done as part of usual care. Boxes marked with R are tests done for research only.

Test	BL	1m	3m	6m	9m	12m	18m	24m
Resting Metabolic Rate (MEDGem Analyzer)	UC			R		R		R
Body Fat % by Bioelectrical Impedance Analysis (RJL Systems)	UC			R		R		R
Height	UC							R
Weight	UC	UC	UC	UC	UC	UC	UC	UC
Waist Circumference	UC			R		R		R
Blood draw	R		R	R		R	R	R

Monitoring of Side Effects to study medication

Monitoring for side effects will be performed at each visit. Report of suicidal ideation will lead to study discontinuation and withdrawal from medication. Endpoint will be considered reached in this instance.

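### No rule says how the 3-month weight plateau in the primary endpoint is scored across the 6-month gaps between weights after month 12

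*Combined protocol and SAP*

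**What the plan says.** - **Definition.** The Primary endpoint section requires "Weight plateau (defined as weight gain or < 3 lbs weight loss) for at least 3 months", together with a BMI still above 39.9 kg/m² and continuing co-morbidity, at any time in the 24 months after surgery. The Treatment Group section uses the same 3 lb threshold but words the duration differently: "for 3 consecutive months, remains above a BMI of 39.9". It adds that "At any point during this course of follow up, a determination can be made that the primary outcome event has occurred".
- **Visits.** The Treatment Group section gives "standard post-operative surgical follow up at months 1, 3, 6, 9, 12, 18, and 24". The section on other measures obtained by chart review says "Weight is measured at every clinic visit and will be captured for the study at the time points in the table below". That table has baseline and months 1, 3, 6, 9, 12, 18 and 24. Weight is marked UC at each of them: "Boxes marked with UC are tests that are done as part of usual care".
- **Month 15.** Safety Monitoring lists a month-15 physician visit for participants after surgery. The Treatment Group section and the table do not. The Statistical analysis section says that weights from clinic visits are among the study outcomes uploaded.
- **Controls.** The Control Group section describes matched historical patients, assessed by retrospective review.
- **Expected timing.** The rationale is that continuing Qsymia after surgery would "potentially extend the weight loss horizon so that the probability of the typical weight loss plateau at 12-18 months is decreased".
- **Analysis.** The Statistical analysis section compares the proportions reaching the endpoint after 24 months. No section says how weights 6 months apart are turned into a 3-month plateau, or how missed or off-schedule weights are handled.

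**The concern.** The criterion has a 3-month time scale, but after month 12 the captured weights are 6 months apart. Two analysts following the plan could apply 3 lb to the whole interval, scale it to the interval's length, or look for an interim weight, and so count different events. This falls in the period when the rationale expects the plateau and expects Qsymia to act.

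Two things are at stake. First, if late plateaus face a stricter test than early ones, a treatment that only postpones the plateau could appear to prevent it. Second, cases are followed prospectively and controls are read from charts. If extra weights count for cases only, the two groups have unequal chances of being scored as events.

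**Working it through.** The plan gives no figure on this point to reproduce. The check compares the criterion with the visit list. It assumes throughout that the BMI and co-morbidity criteria are met and that weights carry no measurement error.

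**1. Intervals available.** From months 1, 3, 6, 9, 12, 18 and 24, consecutive intervals are 2, 3, 3, 3, 6 and 6 months. The 1–3 interval is too short for a 3-month plateau. Intervals 3–6, 6–9 and 9–12 fit it exactly; 12–18 and 18–24 are twice as long.

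**2. What is already settled.** A 6-month interval with a gain, or a loss under 3 lb, satisfies a duration of 3 months or more. The unsettled case is a net 6-month loss of 3 lb or more that contains a 3-month plateau.

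**3. Implied loss rate.** Suppose that under 3 lb is a total over the plateau, and that it is applied between consecutive listed visits (an assumption, since no section says so):
- 3-month interval: 3/3 = 1.0 lb/month
- 6-month interval: 3/6 = 0.5 lb/month
- 9–18 interval, if month 12 is missed: 3/9 = 0.33 lb/month

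**4. Two patients who slow to the same rate, 0.75 lb/month.**
- Patient A slows at month 9. Loss over 9–12 is 3 × 0.75 = 2.25 lb, under 3: event.
- Patient B loses 18, 9 and 4.5 lb over 3–6, 6–9 and 9–12, then slows at month 12. Loss over each of 12–18 and 18–24 is 6 × 0.75 = 4.5 lb, not under 3: non-event. Yet every 3-month window after month 12 shows 2.25 lb, which meets the written definition.

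**5. Effect of month 15.** If month-15 weights count, Patient B's 12–15 and 15–18 losses are 2.25 lb each: event. If month-15 weights count for cases only, the same weight history is an event in a case and a non-event in a control. No section lists a visit between months 18 and 24, so that gap stays unresolved in both groups.

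**6. A scaled threshold.** Let a and b be the losses in the two 3-month halves of a 6-month interval. If a ≥ 3 and b ≥ 3, then a + b ≥ 6. So a + b < 6 implies that at least one half has a loss under 3 lb. On the 3-month-total reading, scoring a net 6-month loss under 6 lb as a plateau therefore adds none that the plateau criterion would not count. For Patient B, 4.5 < 6: event. The rule still misses some: a loss of 10 lb then 0 lb totals 10 and is not scored, although the second half is flat.

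**7. The other reading.** The Treatment Group wording can also mean under 3 lb in each of three successive months, which allows up to just under 3 × 3 = 9 lb in total. No two listed post-operative weights are one month apart, so the table cannot score that reading directly.

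**8. Weight of one patient.** The sample size section plans 25 experimental and 20 control subjects; the Statistical analysis section recruits to 20 cases. One reclassified patient is 1/25 = 4 points or 1/20 = 5 points.

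**The case against.** The strongest reply is that the plan is less empty than it looks. A duration of 3 months or more already covers the clearest late plateaus, those with regain or nearly flat weight. The table may not be the endpoint dataset: the capture sentence sits under a heading about other measures, weight is taken at every clinic visit, the clinician may make the determination at any time, and a month-15 visit is listed. If those weights count, 12–18 splits into two 3-month intervals for cases. Weight is usual care at every table month, so controls' charts may hold the same months. The endpoint is eligibility for a second operation, so an algorithm that departs from the clinical determination alters the endpoint. And this is a pilot.

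Much of that stands. The halving in step 3 depends on a scoring rule and a reading that the plan does not state. The tension between algorithm and clinical determination is real, and the fix has to report it. But counting month 15 resolves 12–18 for cases only and leaves 18–24 open in both groups. Historical controls were not assessed under this protocol as they were followed, so their events must be derived from charts, and that needs a written rule. Using the same visits in both groups is not necessarily neutral when the premise is that plateau timing differs between them. Although this is a pilot, the plan states a between-group hypothesis on this endpoint and gives power for it.

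A reader might infer that late plateaus cannot be scored at all. The documents do not support that, because a 6-month interval with a gain or a loss under 3 lb qualifies.

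**Conclusion.** The point holds as a gap in the endpoint definition that should be closed before analysis. The criterion cannot be applied uniquely to 6-month intervals with a net loss of 3 lb or more. On the 3-month-total reading, an unscaled comparison between listed visits would hold a plateau starting after month 12 to half the loss rate allowed earlier, so a delayed plateau could be scored as prevented. Counting month-15 weights for cases only would work the other way, giving cases more chances to be scored as events.

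A reader might infer that the comparison is biased towards Qsymia, or that the assumed control failure rate of 0.7 is wrong. The documents support neither. The two mechanisms oppose each other, and the documents give no distribution of late weight change, no count of patients meeting the BMI and co-morbidity criteria, and no description of how complete the control charts are. Net direction and size are therefore not estimable. The only firm scale is 4 to 5 percentage points per reclassified patient.

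**What to change.** For the analysis endpoint only, leaving the clinical determination on a second operation unchanged:

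1. Reconcile the plateau wording between the Treatment Group and Primary endpoint sections, including whether the 3 lb figure is a 3-month total or a monthly one. Reconcile month 15 across the Treatment Group section, the schedule table, Safety Monitoring and Statistical analysis.
2. Score the comparative primary endpoint with one prespecified algorithm on the same visit months in cases and controls. Use the same visit-window and missed-visit rule in both groups (for example, for a 9–18 gap when month 12 is missed), and report missed or bridged intervals by group.
3. If the 3-month-total reading is confirmed, score a 6-month interval as a plateau when the net loss is under 6 lb.
4. Report a sensitivity analysis that adds month-15 and unscheduled weights and any event determined clinically at a visit. List every patient for whom the clinical determination and the algorithm differ.

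The cost is SAP wording and one scoring program run on chart weights, with no added visits. Two drawbacks remain. Some plateaus inside a 6-month gap will still be missed, though by the same rule in both groups, and the analysis score may differ from the clinical determination for some patients.

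### The co-morbidity criterion of the primary endpoint has no definition, assigned assessment or data source, and is likely to be ascertained differently in Qsymia patients and historical controls

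*Combined protocol and SAP*

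**What the plan says.** The Primary endpoint section requires three things together at some point in the 24 months after surgery: a weight plateau, a BMI still above 39.9 kg/m², and a third criterion that begins "Continues to have obesity associated co-morbidities (Co-morbidities include hypertension, type 2 diabetes mellitus or pre-diabetes, hyperlipidemia, metabolic syndrome, obstructive sleep apnea" and goes on to further conditions. Eight kinds of condition are listed. No diagnostic threshold, minimum number, rule for resolution, assessor or data source is given.

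For treated patients, the Treatment Group section says: "At any point during this course of follow up, a determination can be made that the primary outcome event has occurred". It repeats the three criteria without adding detail and does not say who makes the determination.

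For controls, the Control Group section says: "They will be a historical control group who had surgery prior to the commencement of the proposed study (retrospective review"). On comparability it adds: "They will be matched to subjects in the treatment group on age, sex, ethnicity, and BMI".

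The test table under Blood Measures covers metabolic rate, body fat, height, weight, waist and a blood draw. The blood is taken at baseline and at intervals up to "18 months and 24 months and stored for use in later analysis". No row of the table is assigned to co-morbidity. Elsewhere, the side-effect monitoring section provides a basic metabolic panel (for acidosis) and vitals (for drug monitoring) at visits. The Statistical analysis section names weight as the study outcome to be entered in the database, in a list that is left open-ended.

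**The concern.** Because all three criteria must hold, the third can decide the outcome alone: a patient who has plateaued above the BMI limit is a non-event once the co-morbidities are judged resolved. Criteria 1 and 2 rest mainly on weight, which the test table marks as usual care at every listed visit. Criterion 3 is the component that needs judgement, and it is the one left undefined.

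That would matter less if both groups were observed in the same way. Here one group is followed forward, on a known drug, with visits, questionnaires and chemistry panels. The other is reconstructed from records made before the study began. Two patients with the same clinical course could be scored differently because of how they were observed. Matching on age, sex, ethnicity and BMI does not address this, nor do the planned adjusted models, because the difference lies in how the outcome is measured and not in who was enrolled.

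**Working it through.** **1. What the text establishes for each group.**

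| Item | Qsymia group | Controls |
|---|---|---|
| Timing of the determination | During follow-up, at any point | After the fact |
| Group known to the assessor | No masking described | No masking described |
| Source for criterion 3 | Not stated | Not stated beyond retrospective review |
| Rule for continuing or resolved | None | None |
| Rule for missing information | None | None |
| Extra observation under the plan | Vitals and basic metabolic panel at visits, for drug safety | None |

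The absence of a rule is a matter of text. The difference in ascertainment is a strong inference from the first and last rows.

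**2. The plan's own power figure.** Inputs from the sample size section: failure rates 0.70 (control) and 0.25 (Qsymia), alpha 0.05 (taken as two-sided), uncorrected chi-squared, stated power 0.840.

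Power = Φ[(|p1 − p2| − 1.96·s0)/s1], where s0 is the pooled standard error and s1 the unpooled one.

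- 20 v 20: mean rate 0.475, s0 = 0.1579, s1 = 0.1410. (0.45 − 0.3095)/0.1410 = 0.997, so power = 0.8405. This matches.
- 25 v 20, the sizes written in that section: power = 0.880. This does not match.

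The Statistical analysis section sets a target of 20 cases, so 20 v 20 is used below and 25 v 20 is shown beside it. The mismatch in sizes does not affect the present point.

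**3. Illustration toward Qsymia.** Assume a true event rate of 0.70 in both groups. A share r of Qsymia events is removed only because resolution is credited there, with no corresponding error in controls. The observed Qsymia rate is 0.70 × (1 − r). The chance of a significant result favouring Qsymia comes from summing exact binomial probabilities over all outcomes that the uncorrected chi-squared test rejects in that direction.

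| r | Observed Qsymia rate | Spurious gap | Gap as share of planned 0.45 | 20 v 20 | 25 v 20 |
|---|---|---|---|---|---|
| 0 | 0.70 | 0 | 0 | 2.7% | 2.5% |
| 10% | 0.63 | 0.07 | 16% | 7.1% | 6.8% |
| 20% | 0.56 | 0.14 | 31% | 14.8% | 15.4% |
| 30% | 0.49 | 0.21 | 47% | 26.3% | 29.3% |

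**4. Illustration against Qsymia.** Assume the planned true rates, 0.70 and 0.25. A share r of control events is missed because the old chart does not record the co-morbidity. The observed control rate is again 0.70 × (1 − r).

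| r | Observed control rate | Exact power, 20 v 20 | Exact power, 25 v 20 |
|---|---|---|---|
| 0 | 0.70 | 0.82 | 0.87 |
| 10% | 0.63 | 0.68 | 0.74 |
| 20% | 0.56 | 0.51 | 0.57 |
| 30% | 0.49 | 0.35 | 0.39 |

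The values of r are assumptions. The documents give no misclassification rate for either group.

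**The case against.** The strongest reply is that nothing in the plan says the groups will be scored from different sources. Controls come from the same centre, treated patients follow standard surgical follow-up, and one section is headed as covering measures obtained by chart review. A common chart source is compatible with the text. This stands as far as it goes: the split is inferred. But criterion 3 is not listed under that heading, and a source that is unstated for both groups is itself the gap.

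A reader might go further and infer that the plan credits resolution mainly to the Qsymia group. The documents do not support that. It would need diagnoses to be carried forward unexamined in control charts, which no section says. It would also need study visits to offer treated patients a special route to being judged resolved. The study blood is stored and no lipid, HbA1c or liver test is scheduled. The vitals and metabolic panel bear on blood pressure and glucose at most, and could reveal a continuing condition as readily as a resolved one. Thin control charts would push the other way. So would the on-drug safety events that the side-effect monitoring section treats as the endpoint being reached, if the primary endpoint is meant.

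The size is also open to challenge. The illustration in step 3 puts all the error in one group. If any one listed condition suffices, every condition a patient has must be judged resolved before criterion 3 changes the result, and it may seldom do so. The plan does not say whether one suffices. This limits what can be claimed about magnitude. It does not remove the need for a rule.

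**Conclusion.** The point holds as a defect of definition and comparability. A required component of the primary endpoint has no operational meaning and no stated source, and it will probably be ascertained differently in the two groups. Neither the direction nor the size of any bias is established.

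The tables show only that, with groups this small, modest one-sided error matters: misclassifying 20% of events in one group takes the false-positive chance favouring Qsymia from 2.7% to about 15%, or exact power from 0.82 to 0.51. These figures rest on an assumed error rate, on error confined to one group, on a 0.70 true rate in both groups (first case) or the planned 0.70 and 0.25 (second case), and on 20 per group. If criterion 3 rarely decides the outcome, the real effect is smaller. The plan should be changed, with medium confidence in how much the change would matter.

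**What to change.** - Write one scoring rule for criterion 3, covering presence and resolution, the number of conditions required, and how a treated, controlled condition is scored. This is for endpoint scoring only and leaves the clinical decision on a second operation untouched.
- Apply it in both groups to chart sources that both have: the diagnosis list and active treatment at the date criteria 1 and 2 are met. Do not use study-only data, such as research bloods or study questionnaires, for the Qsymia group.
- State in advance how a silent or incomplete chart is scored, identically in both groups.
- Have the same abstractor score both groups, with group masked where the extract allows.
- Report beside the primary result the proportion meeting criteria 1 and 2 alone, from usual-care weights at visit months common to both groups. The visit lists need reconciling for this: Safety Monitoring includes month 15, while the Treatment Group section and the test table do not.

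The cost is protocol wording, a common chart abstraction and one extra tabulation, with no new tests. Some information on resolution seen only at study visits is given up. Masking will be imperfect, since dates and drug entries can reveal the group, and study clinicians' entries in the clinic chart may still carry over. The result on criteria 1 and 2 alone helps to show how far the conclusion depends on criterion 3.
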